3.3. Introduction

Study JP04 is a Phase 2, global, multicenter, randomized, open-label study for pediatric and adult participants with relapsed or refractory Ewing's sarcoma or Ewing's sarcoma-like tumors. The study will evaluate the benefits of adding abemaciclib to irinotecan and temozolomide.

3.3.1. Study Rationale

Ewing's sarcoma is an aggressive sarcoma of the bone and/or soft tissue, with a peak incidence in adolescents but can occur from infancy to adulthood. A multidisciplinary approach of neoadjuvant chemotherapy, surgery, or radiation (reserved for unresectable tumors) has improved 5-year EFS and OS to 69% and 72%, respectively, in the pediatric population (Leavy et al. 2008). However, 30% to 40% of those who present initially with localized or metastatic disease will ultimately suffer a disease recurrence (Leavey et al. 2008). Time to relapse is typically short: a median of only 1.4 years for patients with initial localized disease, and 12 months for those initially metastatic (Leavey et al. 2008). The prognosis for patients after disease relapse is dismal with 5-year OS rate of only 13% and mOS of only 7 months following progression (Stahl et al. 2011; Diaz-Beveridge et al. 2015). Long-term survivors of relapsed Ewing's sarcoma are rare. There is an urgent unmet need for new therapeutic strategies to improve this dismal prognosis.

To date, salvage therapies remain inadequate and there is no single standard treatment for relapsed or refractory Ewing's sarcoma. Among the accepted regimens, although irinotecan and temozolomide have demonstrated some of the highest response rates of up to 63% and a 2-year OS rate of 36% in Ewing's sarcoma patients (Casey et al. 2009; Raciborska et al. 2013; Ju et al. 2021), these dismal outcomes highlight the need for continued improvements. Despite large multinational studies of novel combinations, treatment of relapsed Ewing's sarcoma relies entirely on chemotherapeutic agents that have been largely unchanged for decades. This highlights a need for rationale-targeted therapies beyond conventional cytotoxic chemotherapy. Based on the role of CDKs in the activation of DNA-damage signaling and repair, along with the evidence of CDK pathway aberrations in Ewing's sarcoma, it is hypothesized that the addition of abemaciclib to irinotecan plus temozolomide may be of potential benefit for treatment of Ewing's sarcoma.

Study JP04 is designed to investigate the efficacy of abemaciclib in combination with irinotecan and temozolomide for the treatment of participants with relapsed or refractory Ewing's sarcoma or Ewing's sarcoma-like tumors.

3.3.2. Background

3.3.2.1. Ewing's Sarcoma

Ewing's sarcoma is an aggressive sarcoma of the bone and/or soft tissue, most common in adolescence but reported from young children to adults. With the current multimodal therapies including dose intensified and interval compressed systemic chemotherapy with surgery and/or radiation, survival has improved for those with localized disease. Unfortunately, patients presenting with metastatic disease at initial diagnosis or those with relapsed disease have little

chance for cure. Even if relapse is limited and localized, the long-term survival is 22% to 24% and even less for patients with distant relapse (Rodríguez-Galindo et al. 2008).

The t(11;22) chromosomal translocation common in Ewing's sarcoma was characterized by Delattre et al. over 20 years ago, and further research demonstrated that the resulting fusion protein EWSR1-FLI1 is expressed by 95% of Ewing's sarcoma tumor cells (Delattre et al. 1994). More recently, alternative fusion partners have been identified, which are classified as Ewing's sarcoma-like tumors. Ewing's sarcoma-like tumors are undifferentiated round cell tumors that mimic classical Ewing's sarcoma in terms of morphology. However, their defining genetic features are alternative rearrangements, such as *CIC*-rearrangements, *BCOR*-rearrangements, and *EWSR1*-non-ETS rearrangements, among others (Renzi et al. 2019). The response to standard treatment can vary among Ewing's sarcoma-like subtypes (Renzi et al. 2019). Thus, additional research is needed to understand how to tailor treatment for tumors with unique rearrangements.

In classical Ewing's sarcoma, the EWSR1-FLI1 fusion is responsible for the malignant Ewing's sarcoma phenotype and, therefore, was initially considered an ideal target. However, thus far, no EWSR1-FLI1-directed therapies have delivered a meaningful clinical benefit (Grohar et al. 2017). This lack of efficacy may result from a lack of EWSR1-FLI1 enzymatic activity (Riggi et al. 2021). The search for actionable targets in Ewing's sarcoma remains a priority with current approaches relying on alternative mechanisms, such as cell-cycle inhibition.

In Ewing's sarcoma, the cell cycle is deregulated by multiple mechanisms and Cyclin D1 has been shown to be a direct target of EWSR1-FLI1 (Matsumoto et al. 2001; Kowalewski et al. 2011). Ewing's sarcoma tumors frequently carry mutations in cell-cycle regulators, including overexpression of cyclin D1 (*CCND1*), amplification of *CDK4*, losses or low expression of *CDK* inhibitors (Kennedy et al. 2015) making *CDK4/6* inhibition a logical target. Further research supporting exploration of *CDK4* and *6* inhibition in Ewing's sarcoma was provided by demonstration of Ewing's sarcoma cell line sensitivity to *CDK4/6* inhibition and slowed growth in xenograft models after treatment with *CDK4/6* inhibitors (Kennedy et al. 2015).

3.3.2.2. Abemaciclib

[figure not shown]
Abemaciclib is an orally administered, potent, and selective inhibitor of *CDK4* and *6* currently approved for the treatment of hormone receptor-positive, human epidermal growth factor receptor 2-negative, advanced breast cancer as monotherapy and in combination with endocrine therapies (Dickler et al. 2017; Goetz et al. 2017; Sledge et al. 2017; Johnston et al. 2019).

A goal of inhibiting *CDK4* and *6* is to prevent cell-cycle progression through the G1 restriction point, thus arresting tumor growth. Cyclin-dependent kinases 4 and 6 participate in a complex with D-type cyclins to initiate the transition through the G1 restriction point, which controls entry into S phase and is essential for maintaining control of cell division (Sherr 1996; Ortega et al. 2002).

The proposed investigation of abemaciclib in the treatment of Ewing's sarcoma is based on both the mechanism of action and nonclinical data supporting critical involvement of the *CDK4* pathway in Ewing's sarcoma tumors. Additionally, preclinical models demonstrate that cancers such as Ewing's sarcoma with D-type cyclin-activating features, genomic aberrations known to

elevate D-cyclin levels, are sensitive to abemaciclib (Gong et al. 2017; Dowless et al. 2018). In the cell-derived xenograft Ewing's sarcoma model A673 (derived from a 15-year-old patient), of the 6 animals treated with the triplet combination of abemaciclib, irinotecan, and temozolomide, 1 had a partial regression and 5 had SD, while the 6 animals treated with temozolomide and irinotecan experienced progressive disease (Dowless et al. 2018). The combination was well tolerated based on evaluation of body weight. In addition, durable responses with abemaciclib in combination with irinotecan and temozolomide have been reported in other Ewing's sarcoma models (Dowless et al. 2018).

A673 Ewing's sarcoma CDX model in mice treated with vehicle, abemaciclib (daily for 28 days), temozolomide and irinotecan (daily for 5 days, rest for 16 days, then daily for 5 days), or abemaciclib, temozolomide, and irinotecan (same schedules for each drug as above). Treatment started on approximately Day 15. (A) Tumor volume over time; (B) tumor response assessment at Day 31 (Modified from Dowless et al. [2018]).

Abbreviations: CDX = cell-derived xenograft; PD = progressive disease; PR = partial response; SD = stable disease; T/C = treated tumor size divided by control tumor size; TMZ = temozolomide.

3.3.2.3. Irinotecan

Irinotecan is a topoisomerase I inhibitor frequently used in combination with temozolomide for treatment of relapsed or refractory Ewing's sarcoma based on improvements in EFS (Casey et al. 2009). The irinotecan AE profile is well documented and predictable. Notably, irinotecan can cause myelosuppression and early and late forms of diarrhea; early diarrhea may be accompanied by cholinergic symptoms (Irinotecan US Package Insert 2020).

3.3.2.4. Temozolomide

Temozolomide is a DNA-alkylating agent widely used in combination with irinotecan in pediatric solid tumors (Casey et al. 2009). The safety profile of temozolomide is well established and predictable and is known to cause myelosuppression and hepatotoxicity (Temozolomide US Package Insert 2019). Per the SmPC, temozolomide is indicated for children from the age of 3 years, adolescents and adult patients; however, temozolomide is globally also used in children

under 3 years of age for the treatment of Ewing's sarcoma and other solid tumors as described in several publications (Wagner et al. 2004; Casey et al. 2009; Grill et al. 2013; Di Giannatale et al. 2014; Kurucu et al. 2015; Moreno et al. 2017; Le Teuff et al. 2020; Defachelles et al. 2021). See also Section 3.5.5 for dose justification.

3.3.2.5. Irinotecan and Temozolomide Combination

Although alone, each agent has minimal activity against Ewing's sarcoma, the combination of irinotecan and temozolomide demonstrated schedule-dependent synergy and antineoplastic activity in pediatric patients with relapsed solid tumors including Ewing's sarcoma (Houghton et al. 2000; Wagner et al. 2004, 2007). The combination delivered objective response rates of 29% with some CRs and a mean duration of response of 30 weeks in patients with relapsed or refractory Ewing's sarcoma patients, including many who were metastatic at initial presentation (Wagner et al. 2007). Casey et al. reported a time to progression of 16.2 months in pediatric and adult patients with Ewing's sarcoma recurrence when treated with this combination (Casey et al. 2009).

The combination of irinotecan and temozolomide is tolerated with manageable toxicities, including diarrhea, colitis, neutropenia, and thrombocytopenia (Casey et al. 2009).

3.3.3. Benefit/Risk Assessment

Due to the dismal prognosis of relapsed or refractory Ewing's sarcoma, there is an urgent need for new strategic combinations incorporating targeted therapies into already accepted chemotherapy regimens. The irinotecan and temozolomide combination is a preferred regimen for relapsed or refractory Ewing's sarcoma. Thus, all participants will receive a known active therapy for relapsed or refractory Ewing's sarcoma. Participants in Arm A will also receive abemaciclib. The addition of abemaciclib may result in improved clinical benefit compared to irinotecan and temozolomide without abemaciclib.

The combination of abemaciclib, irinotecan, and temozolomide was preliminarily characterized in the pediatric I3Y-MC-JPCS (JPCS) Phase 1b study. This combination exhibited a manageable safety profile. Treatment with the combination of abemaciclib, irinotecan, and temozolomide is expected to be tolerated and may delay disease progression. Prolonged disease control may also delay the need for further cytotoxic chemotherapy.

Based on the overlapping toxicities of abemaciclib, irinotecan, and temozolomide, these are considered the most significant risks on JP04:

- Grade ≥ 3 diarrhea
- Grade 3-4 neutropenia
- Grade 3-4 thrombocytopenia
- febrile neutropenia
- hepatotoxicity
- ILD/pneumonitis, and
- VTE.

Signs and symptoms of deep vein thrombosis and pulmonary embolism are closely monitored throughout the study and guidance for venous thromboembolic events is provided in Section 3.9.3.1.3 and dose modifications are provided in Section 3.7.8.3.2.

Hematology, hepatic, and renal function tests are regularly monitored throughout the study. Increased susceptibility to infection will be mitigated through regular hematology laboratory testing and monitoring of vital signs. These activities enable appropriate investigator oversight, including the identification and management of AEs.

This combination of abemaciclib, irinotecan, and temozolomide was found to be tolerable in Study JPCS, a Phase 1b dose escalation trial in pediatric participants with relapsed or refractory solid tumors. In Study JPCS, hematological toxicities, such as neutropenia and thrombocytopenia, along with gastrointestinal toxicities, such as diarrhea and vomiting, were common AE events at the RP2D. The RP2D combination was abemaciclib 55 mg/m² BID, irinotecan 50 mg/m²/day for 5 days along with temozolomide 100 mg/m²/day for 5 days.

Appropriate safety assessments, on-study monitoring, and AE management are detailed in Section 3.9.3 and Section 9.2 of the CAMPFIRE Master Protocol. Risks are minimized with deliberate inclusion and exclusion criteria to ensure the safety of eligible participants selection. Additionally, participants will have vital sign monitoring, hematology and hepatic monitoring, and assessment of participant-reported symptoms monitored according to the SoA (Section 3.2). To begin each cycle of therapy, participants will be required to meet minimum laboratory criteria prior to the start of each cycle. When necessary, doses will be modified and/or omitted if required per Section 3.7.8.

More information about the known and expected benefits, risks, SAEs, and reasonably anticipated AEs of abemaciclib are to be found in the IB.

More detailed information about the known and expected benefits and risks of irinotecan and temozolomide may be found in the Patient Information Leaflet, Package Insert, and/or Summary of Product Characteristics.

Overall, the potential risks of the abemaciclib in combination with irinotecan and temozolomide are justified in consideration of the measures to minimize these risks and the potential benefit of improved disease control in participants with relapsed or refractory Ewing's sarcoma – a disease with a terrible prognosis and need for effective therapeutic options.

3.3.3.1. Benefit/Risk Assessment of COVID-19

Ensuring the health and safety of research participants, reducing the burden on the healthcare system, and upholding the integrity of clinical trial data are of the utmost importance. Based on the poor survival and lack of therapeutic options for patients with relapsed or refractory Ewing's sarcoma, the potential benefits study participants may receive outweigh the risks they may encounter by being on-site at the facility to receive treatment during the COVID-19 pandemic. Whether these patients seek treatment in a clinical trial setting or in a standard healthcare setting, the risk of COVID-19 infection will be present. Activities in this trial were designed to reflect the standard of care activities for this patient population. However, there are some additional

visits to ensure patient safety and to meet the trial objectives. These additional visits are not considered to pose a significant increase in risk, since standard local hospital/clinic procedures to prevent the spread of COVID-19 will be in place.

3.4. Objectives and Endpoints

Table JP04.5 shows the objectives and endpoints of the study.

Table JP04.5. Objectives and Endpoints

Objectives	Endpoints
Primary	

 To characterize the efficacy of abemaciclib in combination with irinotecan + temozolomide 	
 PFS as determined by BIRC using RECIST 1.1
Secondary	

 To evaluate the safety profile of abemaciclib, irinotecan, and temozolomide combination 	
 Safety (including but not limited to): TEAEs, SAEs, deaths, laboratory abnormalities, vital signs, and physical examinations

 To characterize the clinical activity of abemaciclib, irinotecan, and temozolomide combination 	
 OS ORR DoR DCR PFS as determined by investigator assessment using RECIST 1.1

 To characterize the PK of abemaciclib in combination with irinotecan + temozolomide 	
 Concentrations of abemaciclib

 To assess the acceptability and palatability of the age-appropriate tablet and/or granule drug product, including dispersed tablets and/or granules 	
 Assessment of tablet, granule, or dispersed drug product presentation, including acceptability and palatability
Exploratory	

 To explore the relationship between abemaciclib concentrations and clinical outcomes 	
 Outcomes such as clinical efficacy and safety

 To explore correlation of biomarkers to clinical outcomes 	
 Outcomes such as clinical efficacy and/or exposure parameters

Abbreviations: BIRC = blinded independent review committee; DCR = disease control rate; DoR = duration of response; ORR = objective response rate; OS = overall survival; PFS = progression-free survival; PK = pharmacokinetics; RECIST 1.1 = Response Evaluation Criteria in Solid Tumors, Version 1.1 (Eisenhauer et al. 2009); SAEs = serious adverse events; TEAE = treatment-emergent adverse event.

3.5. Study Design

[figure not shown]
3.5.1. Overall Design

Study JP04, combined with Protocol J1S-MC-JAAA (hereinafter referred to as the CAMPFIRE Master Protocol), is a multicenter, randomized, open-label, Phase 2 study in participants with relapsed or refractory Ewing's sarcoma.

Participants will be randomized 2:1 between 2 treatment arms and will be treated until disease progression or having met other discontinuation criteria.

Figure JP04.1 illustrates the study design.

Figure JP04.1. Illustration of study design.

Abbreviations: n = number of participants; PFS = progression-free survival.

^a One futility analysis will occur after approximately CCI events have been observed. See Section 3.10.3.5.2.

3.5.1.1. Criteria to Begin Day 1 of Subsequent Cycles (C2 and beyond)

CCI	

Treatment may be suspended for a maximum of 21 days to allow a participant sufficient time for recovery from study treatment-related toxicity. In exceptional circumstances, a delay >21 days is permitted upon agreement by Lilly CRP/CRS.

3.5.2. Number of Participants

At least 45 participants will be enrolled. CCI

3.5.3. End of Study Definition

End of the study is the date of the last visit or last scheduled procedure shown in the Schedule of Activities (Section 3.2) for the last participant.

Study completion is the date of the last visit or last scheduled procedure associated with the final evaluation of all primary and secondary objectives. Investigators will continue to follow the SoA (Section 3.2) for all participants until notified by Lilly that study completion has occurred.

3.5.4. Scientific Rationale for Study Design

The overall rationale for the study design is described in Study Rationale (Section 3.3.1) and in the Statistical Considerations (Section 3.10) sections. Dose selection details can be found in Section 3.5.5.

A randomized, controlled design is being used in this study. Randomization minimizes systematic bias in the selection and assignment of participants to study therapy and provides justification for inferential statistical methods to be used on data from this study. All randomized participants will receive irinotecan plus temozolomide, a standard of care in the treatment of relapsed or refractory Ewing's sarcoma. Participants assigned to Arm A will also receive abemaciclib. However, participants in the control arm will not receive matching placebo. Therefore, participants and investigators will not be blinded to treatment assignment. This minimizes the burden placed on pediatric participants, and is additionally supported by the potentially unblinding adverse event profile of abemaciclib. A combination of randomization, a primary endpoint derived from a blinded, independent review committee, and a blinding plan to strictly control the study team's access to aggregate data will protect the scientific integrity of the study and provide reliable evidence on the effectiveness of the study interventions.

Additionally, the primary analysis will utilize a Bayesian-augmented control arm to incorporate historical data, minimizing the number of participants required to be randomized.

In this study, collection of demographic information includes race and ethnicity. The scientific rationale is based on the need to assess variable response in safety and/or efficacy based on race or ethnicity.

3.5.5. Justification for Dose

Irinotecan and Temozolomide

The combination of irinotecan and temozolomide has been reported with a range of doses for both drugs in both children and adults. In several Ewing's sarcoma trials, temozolomide 80-150 mg/m²/day ×5 days with irinotecan 10-20 mg/m²/day ×5 days (sometimes repeated 2 consecutive weeks) has demonstrated tolerability and efficacy (Wagner et al. 2007; Casey et al. 2009; McNall-Knapp et al. 2010; Wagner et al. 2010; Bagatell et al. 2011; Hernández-Marqués et al. 2013; Palmerini et al. 2018). Importantly, different schedules of irinotecan administration in children with relapsed rhabdomyosarcoma showed that a shorter course of 50 mg/m²/day ×5 days is equivalent to the longer, more protracted schedule of 20 mg/m²/day for 10 days thus reducing participant and caregiver burden of frequent clinic visits for IV infusions (Mascarenhas et al. 2010). Therefore, in this study, temozolomide 100 mg/m²/day and irinotecan 50 mg/m²/day will be administered on Days 1 through 5 of a 21-day cycle. These doses, in combination with abemaciclib, were tolerated in the Phase 1b JPCS study.

Abemaciclib

In Study JPCS, abemaciclib was administered at 2 dose levels in combination with temozolomide and irinotecan: 55 and 70 mg/m² BID. These doses were originally selected for exploration based on the BSA-adjusted adult dose used in abemaciclib combination studies. Abemaciclib is predominantly cleared by CYP3A4, which is expected to have matured after the first year of life (Bartelink et al. 2006). Therefore, between the age of 1 to 18 years, CYP-mediated metabolism is largely dependent on liver volume, which is better correlated with BSA rather than body weight (Bartelink et al. 2006). CCI

Based on the safety, tolerability, and PK of the drug combination in Study JPCS, the abemaciclib dose of 55 mg/m² was declared to be the RP2D when given together with irinotecan 50 mg/m²/day ×5 days and temozolomide 100 mg/m²/day ×5 days in 21-day cycles.

Study JP04 includes both adults and pediatric participants. CCI

3.6. Study Population

3.6.1. Inclusion Criteria

Participants are eligible to be included in the Study JP04 only if they meet all of the inclusion criteria in Section 6.1 of the **CAMPFIRE Master Protocol** and the following criteria:

Age and Weight

[35] Participants aged 1 to <40 years

[36] Body weight ≥ 10 kg

Disease and Participant Characteristics

[37] Eligibility will be based on a diagnosis of Ewing's sarcoma or Ewing's sarcoma-like tumor by institutional pathologist at time of original diagnosis. The original pathological report is required. Repeat biopsy at progression is not required

[38] Must be able to swallow and/or have a gastric/nasogastric tube

a) Participants in the European Union must be able to swallow intact capsules

[39] If on systemic steroids at study entry, the dose must be stable or decreasing during the 7 days prior to C1D1

[40] Life expectancy of at least 8 weeks and able to complete at least 1 cycle of treatment

[41] Participants/caregivers are able and willing to make themselves available for the duration of the study and are willing to follow study procedures, including adherence to the PK sampling schedule

3.6.1.1. Exceptions to the CAMPFIRE Master Protocol Inclusion Criteria

For Study JP04, the below inclusion criteria should be used in place of the CAMPFIRE Master Protocol inclusion criteria of the corresponding number.

[1] Refractory disease or confirmed radiological progression or recurrence following first or later line of treatment of Ewing's sarcoma or Ewing's sarcoma-like tumor.

a. Must have one measurable or evaluable lesion per RECIST 1.1 (Eisenhauer et al. 2009)

[3] Adequate performance status based on age

a) For participants <16 years of age, a Lansky score ≥ 50 , or

b) For participants ≥ 16 years of age, a Karnofsky score ≥ 50

Note: Participants who are unable to walk because of paralysis, but are up in a wheelchair, will be considered ambulatory for the purpose of assessing the performance score

[4] Participants must have discontinued all previous treatments for cancer or investigational agents as shown below and must have recovered from the acute effects to Grade ≤ 1 at the time of

enrollment, unless otherwise noted (Grade ≤ 2 for alopecia, decreased tendon reflex, and residual peripheral sensory neuropathy are acceptable) or as specified in Inclusion Criterion 5. For agents with known AEs occurring beyond the required wait period outlined in the table, this period must be extended until after the time during which the AE is known to occur. For additional therapies not mentioned in the table, including targeted therapies, consult with the Lilly CRP/CRS for the appropriate length of time prior to the first dose of study treatment.

Previous Treatment	Length of Time Prior to First Dose of Study Treatment
Cytotoxic and myelosuppressive chemotherapy	≥ 21 days after myelosuppressive or cytotoxic chemotherapy ≥ 42 days if prior nitrosourea
Hematopoietic growth factors	≥ 14 days after long-acting growth factor (e.g., pegfilgrastim) ≥ 7 days for short-acting growth factor
Cellular therapy	≥ 42 days after cellular therapy (e.g., modified T or NK cells)
Interleukins, interferons, and cytokines	≥ 21 days after interleukins or interferon and cytokines (other than hematopoietic growth factors)
Radiotherapy	≥ 14 days after small port (i.e., local palliative) ≥ 84 days after large-field ($\geq 50\%$ of pelvis or TBI) ≥ 42 days for other substantial bone marrow radiation
Autologous stem cell infusion	≥ 84 days
Corticosteroids	≥ 14 days after systemic corticosteroids (≥ 5 days) to modify immune AEs. Note: Participants on chronic replacement or a stable/decreasing dose for at least 7 days may be eligible (consult Lilly CRP/CRS)
Live vaccines	≥ 28 days after last live vaccine (seasonal flu vaccines that do not contain a live virus are permitted)

Abbreviations: AE = adverse event; CRP/CRS = clinical research physician/clinical research scientist; NK = natural killer; TBI = total body irradiation.

- [5] The participant has adequate hematologic and organ function ≤ 14 days prior to Day 1 of Cycle 1:

System	Laboratory Value
Hematologic	
Absolute neutrophil count	$\geq 1000/\mu\text{L}$ G-CSF ≤ 7 days prior to C1D1 not allowed Pegfilgrastim ≤ 14 days prior to C1D1 not allowed
Platelets	$\geq 75,000/\text{mm}^3$ Platelet transfusion ≤ 5 days prior to C1D1 not allowed
Hemoglobin	$\geq 8 \text{ g/dL}$ ($\geq 80 \text{ g/L}$) PRBC transfusions ≤ 5 days prior to C1D1 not allowed
Hepatic	
Total bilirubin	$\leq 1.5 \times \text{ULN}$ Exception: $< 3.0 \times \text{ULN}$ for participants with Gilbert Syndrome
ALT and AST	$\leq 3 \times \text{ULN}$ Exception: $\leq 5.0 \times \text{ULN}$ if the liver has tumor involvement

Abbreviations: ALT = alanine aminotransferase; AST = aspartate aminotransferase; C1D1 = Cycle 1 Day 1; G-CSF = granulocyte-colony stimulating factor; PRBC = packed red blood cell; ULN = upper limit of normal.

- Creatinine clearance or calculated GFR $\geq 60 \text{ mL/min/m}^2$ or serum creatinine based on age/gender (see Appendix 5 of the CAMPFIRE Master Protocol) as follows:

Age	Maximum serum creatinine (mg/dL)	
	Male	Female
1 to <2 years	0.6	0.6
2 to <6 years	0.8	0.8
6 to <10 years	1.0	1.0
10 to <13 years	1.2	1.2
13 to <16 years	1.5	1.4
≥ 16 years	1.7	1.5

- [6] Female participants of childbearing potential must have a negative urine or serum pregnancy test within 7 days prior to Cycle 1 Day 1. For France, serum pregnancy test must be performed.
- [7] Women of reproductive potential must agree to use highly effective contraceptive precautions (and avoid sperm donation for males) during the trial. For abemaciclib, females should use contraception for at least 3 weeks following the last abemaciclib dose. After the last dose of irinotecan and temozolomide, females should use contraception for at least 6 months, and male participants with a WOCBP partner should use contraception for at least 3 months. Following last dose of temozolomide treatment, men must refrain from sperm donation per product label.

See [Attachment 7](#) for additional details on contraceptive guidance and the collection of pregnancy information.

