Tumor imaging	X		
 According to RECIST 1.1 Radiologic assessments obtained previously as part of routine clinical care may be used as the baseline assessment if they were done no more than 28 days before C1D1. Perform CT scans of the chest, abdomen, pelvis, and the site of the known lesion(s) if located elsewhere. Same modality will be used throughout study Scans will be performed and reviewed locally, and must be submitted to the sponsor designated facility. See Section 3.9.1
Hematology		X	
 Labs drawn within 7 days of C1D1 can be used for both screening/baseline and C1D1 See Attachment 2 for guidance on sample collection

Procedure	Day relative to C1D1		Instructions
	≤28	≤14	
Clinical chemistry		X	
 Labs drawn within 7 days of C1D1 can be used for both screening/baseline and C1D1 See Attachment 2 for guidance on sample collection
Serum or urine pregnancy test		X	
 Only females of childbearing potential See Attachment 2 for guidance on sample collection A negative serum pregnancy test, or a negative urine pregnancy test within 7 days prior to first study treatment on C1D1 is required. For France, serum pregnancy test must be performed. Local practice and guidelines are applicable
Exploratory biomarkers (tumor tissue collection)	X		
 Archival or fresh tumor sample will be collected, where available. The most recent sample is desired. Relapse or metastatic sample where available is preferred See Attachment 3

Abbreviations: C1D1 = Cycle 1 Day 1; CT = computed tomography; CTCAE = Common Terminology Criteria for Adverse Events (NCI 2017); RECIST 1.1 = Response Evaluation Criteria in Solid Tumors, Version 1.1 (Eisenhauer et al. 2009).

Table JP04.2. On-Study-Treatment Schedule of Activities

Procedure	All Treatment Periods (Cycle = 21 Days)															Notes
	Cycle 1			Cycle 2			Cycle 3			Cycle 4			Cycle 5-n			
Relative Day within Dosing Cycle	1	8	15	1	8	15	1	8	15	1	8	15	1	8	15	
Concomitant medications ^a	X															
Collected continuously throughout studyRecord all premedication, supportive care, and concomitant medicationSee Section 3.7.6
Adverse events ^a	X															
Collected continuously throughout studyCTCAE Version 5.0

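### Criterion 5 counts its transfusion and G-CSF restrictions from C1D1, not from the qualifying blood sample, so a participant can qualify on a supported count

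*Protocol*

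**What the plan says.** Protocol Section 3.6.1.1, criterion 5, sets the requirement, "The participant has adequate hematologic and organ function", and dates it to within 14 days before C1D1. The restrictions on supportive treatment stand in the same table, beside the counts they concern. In the neutrophil row they are "G-CSF ≤ 7 days prior to C1D1 not allowed" and "Pegfilgrastim ≤ 14 days prior to C1D1 not allowed"; in the platelet row, "Platelet transfusion ≤ 5 days prior to C1D1 not allowed". The hemoglobin row has the same 5-day restriction for red cells. None of these is dated from the blood draw. Criterion 4 likewise dates its growth-factor washout from first dose.

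Two notes in Section 3.2 govern the Cycle 1 count. The hematology row of Table JP04.1 says "Labs drawn within 7 days of C1D1 can be used for both screening/baseline and C1D1". Table JP04.2 marks hematology at Cycle 1 Day 1 and asks for collection no more than 3 days before a new cycle. Neither note attaches a Cycle 1 threshold.

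Section 3.3.3 says minimum laboratory criteria apply before every cycle but gives no values. Section 3.5.1.1, which sets start-of-cycle criteria, is headed for Cycle 2 onward. Table JP04.1 has eligibility confirmed before randomization.

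**The concern.** Because the restrictions sit in the count rows, the natural reading is that they keep transfusion or G-CSF from carrying a participant over the threshold. Dated from C1D1, they do so in full only when the sample is drawn on C1D1 itself. For an earlier sample, support can be given just before the draw and still fall outside the restricted period.

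Two things are at stake. First, a participant whose unsupported count is below the stated limit can start myelosuppressive treatment, and Section 3.3.3 names Grade 3-4 neutropenia and thrombocytopenia among the study's most significant risks. Second, SAP Section 7.1.2 takes baseline as the last value before first treatment, and Section 7.9.4 tabulates shifts from baseline grade. If a supported count is that last value, the baseline grade looks milder than the participant's unsupported state, and a later fall reads as treatment-emergent.

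**Working it through.** The plan gives no figure to reproduce; the check is day counting.

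**Inputs.** Let c be the number of days from the qualifying sample to C1D1, and w the restriction length.
- Permitted sample days under criterion 5: c = 0 to 14, which is 15 days.
- w = 5 for platelets and red cells, 7 for G-CSF, 14 for pegfilgrastim (criterion 5).
- Draws reusable as the C1D1 count: c = 0 to 7 (Table JP04.1).
- Draws meeting the start-of-cycle note: c = 0 to 3 (Table JP04.2).

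**Formula.** Support is barred on days w or fewer before C1D1, so the latest permitted day is w + 1 before. For support given on or before the sample day, the shortest gap from support to sample is max(w + 1, c) − c.

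**Results (shortest permitted gap, in days).**

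| Support | w | Any permitted sample (c = 0–14) | Reusable draw (c = 0–7) | Draw within 3 days (c = 0–3) |
|---|---|---|---|---|
| Platelets or red cells | 5 | 0 (c = 6–14; 9 of 15 days) | 0 (c = 6 or 7) | 3 |
| G-CSF | 7 | 0 (c = 8–14; 7 of 15 days) | 1 (c = 7) | 5 |
| Pegfilgrastim | 14 | 1 (c = 14) | 8 (c = 7) | 12 |

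Worked cases:
- Platelets, c = 6: max(6, 6) − 6 = 0.
- G-CSF, c = 7: max(8, 7) − 7 = 1.
- Pegfilgrastim, c = 14: max(15, 14) − 14 = 1.
- Sample on C1D1, c = 0: gaps of 6, 8 and 15 days, so the full restriction holds.

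**What happens after the qualifying sample.**
- c = 8 to 14: the draw is too old to reuse, so a fresh C1D1 count follows. Eligibility has by then been confirmed and the participant randomized, and no stated threshold applies to the new count. A randomized participant stays in the ITT set (Section 3.10.2), even if never treated and replaced (Section 3.10.1).
- c = 4 to 7: Table JP04.1 allows reuse, while Table JP04.2 read alone would require a new draw. The same-day transfusion cases (c = 6 or 7) and the 1-day G-CSF case (c = 7) fall here.
- c = 0 to 3: both notes are met, with shortest gaps of 3 days for transfusion and 5 for G-CSF.

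**The case against.** The strongest reply is that other rules catch most cases. Table JP04.2 calls for a C1D1 count, and the 7-day note can be read as an exception to it; the Germany and Spain texts in Attachment 9 carry both notes together. Seven of the nine same-day transfusion days (c = 8 to 14), and all the same-day G-CSF days, are followed by a fresh count. Criterion 4 requires at least 21 days since myelosuppressive chemotherapy, exclusion 46 lets the investigator exclude severe myelosuppression, and Section 3.3.3 promises laboratory criteria for each cycle. Being free of support at treatment start is also a coherent purpose for a window dated from C1D1.

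Much of this stands, and it limits the point. It does not close the gap. Exclusion 46 carries no number, Section 3.3.3 no values, and the C1D1 count no stated threshold.

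A reader might infer more than the documents support:
- **That no later count is ever taken.** Table JP04.2 marks one at C1D1; only a reused draw within 7 days may stand in for it.
- **That 14 of the 15 sample days measure the exposure.** On c = 1 to 14 the shortest gap is indeed no longer than w. That describes what the wording permits, not how often it happens.
- **That the arm comparison is biased.** The criterion is the same for both arms and is confirmed before randomization, so no systematic difference is expected. With the minimum of 45 randomized 2:1, one participant is 1/30 = 3.3% of Arm A or 1/15 = 6.7% of Arm B, but that is true of any participant.
- **That the boundary mismatch between criteria 4 and 5 admits ineligible people.** Criterion 4 accepts exactly 7 days (short-acting) or 14 days (long-acting), and criterion 5 does not. Both must be met, so the mismatch admits no one.

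**Conclusion.** The point holds in a limited form and merits correction. Criterion 5 dates its sample and its support restrictions differently, and following it exactly can admit a participant on a supported count. Among reusable draws, the shortest gap is 0 days for transfusion (samples 6 or 7 days before C1D1) and 1 day for G-CSF. Pegfilgrastim is marginal: its restriction is as long as the sampling window, a same-day count is impossible, and the shortest gap is 1 day.

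The consequences are for participant safety at treatment start and, where the reused draw is the last before dosing, for the baseline hematology grade. Power, alpha and the primary comparison are unaffected.

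This rests on the addendum text. The detail of Section 3.5.1.1 is redacted and the CAMPFIRE Master Protocol was not available, so a Cycle 1 threshold stated there cannot be ruled out; however, Section 3.6.1.1 says its criteria replace the Master Protocol criteria of the same number. The documents do not say how often candidates receive support in the weeks before C1D1.

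**What to change.** - **Criterion 5:** reconcile the dates so that the support restrictions and the qualifying sample refer to the same day, keeping the existing day counts. The sponsor should choose how.
- **Cycle 1 count:** reconcile the 7-day reuse note in Table JP04.1 with the 3-day collection note in Table JP04.2, and state whether the criterion 5 thresholds apply to the C1D1 count.
- **Minor tidy-up:** make criteria 4 and 5 agree on support given exactly 7 or 14 days before.

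For illustration, dating the present windows from the sample would make the shortest gaps 6 days (transfusion), 8 (G-CSF) and 15 (pegfilgrastim).

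The text change is small. The cost is that a few recently supported candidates repeat a routine blood count or wait some days. The wait depends on the route chosen: if the windows ran back from a sample 14 days before C1D1, the transfusion restriction would reach back 14 + 5 = 19 days and pegfilgrastim 14 + 14 = 28 days, unless the count were repeated nearer C1D1.
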